#### **4. Study Procedures**

- a. Study design, including the sequence and timing of study procedures (distinguish research procedures from those that are part of routine care).

Study Design: After the decision to proceed with shoulder replacement surgery, patients will be asked to participate in this prospective randomized clinical trial.

Study Groups:

- Group 1 will receive interscalene nerve block.
- Group 2 will receive liposomal bupivacaine with local bupivacaine for postoperative analgesia.

Study Procedures:

1. Before Surgery: The Informed Consent process will be completed prior to any data collection. Consent will be completed after explanation of each treatment group and the data to be collected. The following baseline data will be collection prior to surgery:

- Demographics (including age, sex, BMI, work status, living environment)
- Medical and Surgical History
- ASA Physical Status Classification
- Charlson Comorbidity Index Score
- Pain History and Medications
- VAS pain score

2. Randomization: Subjects will be randomized prior to surgery into one of the two perioperative analgesia groups. Randomization will be stratified by gender.

3. Surgery/Inpatient Stay:

- Group 1: Patients in the interscalene nerve block group will be given a single shot block in the preoperative area by a fellowship-trained anesthesiologist. The shot will contain a local anesthetic like 5% Ropivacaine (5 mg/1 mL) with a 44 millimeter 22 gauge needle with the patient in the supine position.
- Group 2: The surgeon at each site will be trained prior to enrollment on the correct way to perform Exparel injections intraoperatively. The surgeon will give patients in the liposomal bupivacaine group the periarticular injection

containing 266 mg of the drug in 40 mL injectable saline in the operating room; local 0.5% bupivacaine-epinephrine will also be used not to exceed dose limits.

- Surgical/Inpatient Data Collection:
  - Pre-op procedure time
  - Surgical time
  - PACU time
  - Admission/Discharge time and date
  - Estimated blood loss
  - Procedures performed
  - Inpatient pain medications administered
  - Patient VAS scores every 6 hours after surgery

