## 5. Inclusion/Exclusion Criteria

### Inclusion Criteria:

Adults age 20-100 years old with degenerative changes of the shoulder joint (documented by radiographs) in patients planning total joint replacement with [name] (PI of this study) at Johns Hopkins Shoulder Service (Columbia, Odenton Clinic sites; HCGH/Bayview/JHH operative sites), with [name] at the University of Texas Sports Medicine and Shoulder Service, with [name] at MedStar St. Mary's Hospital Shoulder Service, and with [name] at William Beaumont Army Medical Center will be included. Patients who require revision surgeries, hemiarthroplasties, or who have chronic pain issues will be included.

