## 7. Study Statistics

- a. Primary outcome variable.

- VAS pain score at 24 hours postop.

- b. Secondary outcome variables.

- VAS scores at all other data points,

- Pain medication consumption (narcotics, NSAIDs, Tylenol)
- Opioid-induced side effects (nausea, vomiting, constipation)
- Length of hospital stay
- 30 day readmission rate.

- c. Statistical plan including sample size justification and interim data analysis.

A power analysis was performed to determine the sample size needed to determine noninferiority between groups with respect to VAS pain score. The minimal clinically important difference of VAS is 1.4 cm^13. The number was found to be 42 patients in each group, for a total n = 84. To ensure we reach this number, each of the 4 sites will aim to enroll 30 patients, to account for drop out.

The age of the two treatment groups will be compared using t-test. Sex distribution and the ASA scores of the groups will be compared using a chi-squared test and a Fisher exact test, respectively.

The median and interquartile range of the VAS scores at each of the time points measured will be tabulated by treatment group, and at each time point the difference between groups will be tested using non-parametric rank sum tests.

We will test the longitudinal trajectory of VAS scores over time, taking into account repeated measurements in the same patients using linear mixed model analysis. Treatment group, time period as a categorical variable, and the interaction between treatment and time period will be included as fixed effects, and patient ID will be included as the random effect. An initial omnibus test will be performed for all treatment and treatment by time interaction effects. If significant, the treatment by time interaction will be tested subsequently for each of the measurement periods.

The association of day of discharge (as a categorical variable) with treatment will be tested using the Fisher exact test.

- d. Early stopping rules.

We will monitor operative and post-operative complications including implant failures, nerve injuries, hematomas, and infections. We do not anticipate issues with these complications, as both techniques are in routine use in our current clinical practice. We did not find any differences in the complication rates in our retrospective cohort analysis.

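### The 24-hour VAS test and the mixed model leave out preoperative VAS and the stratification factor, gender: precision is lost, but no bias is introduced

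*Combined protocol and SAP*

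**What the plan says.** All of this is in the combined protocol and SAP.

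- Section 7a names the primary outcome: "VAS pain score at 24 hours postop".
- Section 7c gives the between-group test: "at each time point the difference between groups will be tested using non-parametric rank sum tests". It names no covariate or stratum.
- Section 7c on the mixed model: "Treatment group, time period as a categorical variable, and the interaction between treatment and time period will be included as fixed effects". Neither preoperative VAS nor gender is listed, and the only random term is one per patient. Sex appears in Section 7 only as a chi-squared comparison of the groups at baseline.
- Section 4a, Before Surgery: "The following baseline data will be collection prior to surgery". The list that follows ends with a VAS pain score.
- Section 4a, Randomization: "Randomization will be stratified by gender".
- Section 5: "Patients who require revision surgeries, hemiarthroplasties, or who have chronic pain issues will be included".
- Section 7c sizes the trial for non-inferiority on VAS, cites an MCID of 1.4 cm and arrives at 42 per group. Section 4 enrols 60 per group and allows for 15% dropout.

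Two things are not stated: whether preoperative VAS counts as one of the mixed model's time periods, and whether the rank-sum test or the mixed model decides the primary comparison.

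**The concern.** A preoperative measurement of the outcome is often the most useful covariate available, and here it is collected anyway. Because revision patients and patients with chronic pain issues are eligible, preoperative pain is likely to vary widely. That makes it a plausible predictor of 24-hour pain, though not a proven one. Gender governs the allocation, so including it in the analysis would match the analysis to the design. If either variable predicts 24-hour VAS, the planned analysis has a larger standard error than it needs. The trial then has a lower chance of reaching its intended conclusion from the same patients.

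**Working it through.** **Inputs from the documents.** Difference of interest 1.4 cm; 42 per arm required; 60 per arm enrolled; 15% dropout, so 60 × 0.85 = 51 per arm.

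**Inputs assumed.** Alpha, power, SD and the correlation r between preoperative and 24-hour VAS are not stated. I take one-sided 0.025, 80% power, a true difference of 0 against a 1.4 cm margin, and r from 0.2 to 0.5.

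**Step 1: the plan's own figure.** With the SD missing, 42 per arm can only be solved backwards: SD = 1.4 × √(42/2) / (z for alpha + z for power).

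- One-sided 0.025, 80% power: 1.4 × 4.583 / (1.960 + 0.842) = 2.29 cm
- One-sided 0.025, 90% power: 1.98 cm
- One-sided 0.05, 80% power: 2.58 cm
- One-sided 0.05, 90% power: 2.19 cm

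The figure of 42 is therefore neither confirmed nor refuted. I use 2.29; only the changes in power below are informative.

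**Step 2: effect of adjustment.** Residual SD = 2.29 × √(1 − r²). SE = residual SD × √(2/n). Power comes from the noncentral t distribution with noncentrality 1.4/SE, giving up 2 degrees of freedom for the two covariates. Equivalent n = 42/(1 − r²).

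| r | Variance removed | SE, 42 per arm | Power, 42 per arm | Equivalent n per arm | Power, 51 per arm |
|---|---|---|---|---|---|
| none (t-test) | 0% | 0.500 | 79.1% | 42 | 86.4% |
| 0.2 | 4% | 0.490 | 80.6% | 43.8 | 87.7% |
| 0.3 | 9% | 0.477 | 82.7% | 46.2 | 89.3% |
| 0.4 | 16% | 0.458 | 85.5% | 50.0 | 91.5% |
| 0.5 | 25% | 0.433 | 89.2% | 56.0 | 94.2% |

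From r = 0.2 to 0.5, the gain is about 1.5 to 10 points at 42 per arm and 1.3 to 8 points at 51.

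**Step 3: the planned test itself.** The t-test stands in for the rank-sum test above. Simulation with normal scores, 42 per arm and a 0.2 SD sex difference gave rank-sum power of about 77% and ANCOVA power of 80 / 82 / 85 / 89% at the four correlations. With r = 0, adjusting a rank test for gender alone moved power from 76.7% to 77.2%, so gender adds little.

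**Step 4: validity.** With no true difference, the two-sided 5% rank-sum test rejected in 4.2 to 4.8% of simulated trials, across r from 0 to 0.5 with and without a gender effect. Type I error is not inflated.

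**Step 5: which adjusted analysis should decide.** One could subtract 1.4 cm from one arm and run a rank ANCOVA. That moves one arm's floor below zero. I simulated right-skewed scores with both arms bounded below at 0, the second arm rescaled so that the true mean difference was exactly 1.4 cm, 42 per arm and r = 0.3. Non-inferiority is then false, and the nominal error is 2.5%.

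| Scores | Margin-shifted rank ANCOVA | ANCOVA |
|---|---|---|
| Strong skew (gamma shape 1.5) | about 15% | about 3% |
| Moderate skew (gamma shape 3) | about 7% | about 3% |

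In the same settings, power to detect that 1.4 cm difference with an unshifted two-sided test was about 62–63% for ANCOVA against 55–56% for rank ANCOVA (strong skew), and 68–69% against 63–64% (moderate skew).

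**The case against.** The strongest reply is that the benefit is conditional and already cushioned. Every input to the power figures except 1.4 cm and the patient numbers is assumed. Eligibility of chronic-pain and revision patients supports a spread in preoperative pain, not a correlation with pain at 24 hours. At r = 0.2 or below the gain is only 1 or 2 points. The 51 per arm expected after dropout already exceeds the 50 that adjustment would be worth at r = 0.4. All of this stands. It limits the size of the point, but a prespecified adjustment still costs almost nothing.

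A second reply is that the sponsor chose ranks for robustness to skew, and that ANCOVA would give this up and lose power. A reader might infer this from runs in which one arm is shifted by the margin. It does not survive once both arms share a floor at zero: in the skewed cases simulated, ANCOVA had more power for a real 1.4 cm difference, and the shifted rank analysis exceeded its nominal error. Keeping a rank test as a sensitivity analysis is still reasonable.

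A third reply is that preoperative VAS may be one of the mixed model's time periods, so that the model already uses it in part. The plan does not say. Either way the 24-hour rank-sum test remains unadjusted.

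**Conclusion.** The point holds as one of lost efficiency. Neither the 24-hour test nor the mixed model's listed fixed effects include preoperative VAS or gender. With SD 2.29 cm and one-sided 0.025 assumed, adjustment would raise power from 79% to between 81 and 89% at 42 per arm, and from 86% to between 88 and 94% at 51, for r from 0.2 to 0.5. Nearly all of this comes from preoperative VAS. If r is near zero, nothing is gained.

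A reader might go further and infer that ignoring the stratification factor biases the comparison or inflates its error rate. The documents do not support that: the arms are randomised, and the rank-sum test holds its level under the null of no difference. Nor does the omission by itself put the stated sample size at risk.

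Two neighbouring matters should be kept apart. First, calling the rank-sum test valid refers only to the null of no difference. With no margin applied, it cannot by itself show the non-inferiority for which the trial is sized. Second, the mixed model states no residual covariance beyond the patient effect. That is a minor issue and affects only the secondary longitudinal test.

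**What to change.** In Section 7c:

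1. Name the deciding 24-hour analysis: an ANCOVA of 24-hour VAS on treatment, preoperative VAS and gender, or the 24-hour contrast from the mixed model with the same covariates. Report the adjusted difference in cm with its confidence interval, for comparison with 1.4 cm.
2. Add preoperative VAS and gender to the mixed model's fixed effects, and state that preoperative VAS is a covariate and not a time period.
3. Keep the rank-sum test, or an unshifted covariate-adjusted rank test, as a supporting sensitivity analysis. Do not let a margin-shifted rank ANCOVA decide non-inferiority.
4. Give a rule for missing preoperative VAS.
5. As a minor addition, state the number of time periods and the residual covariance in the mixed model.

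The cost is SAP wording. Both covariates are already collected, so no patients or assessments are added. The downsides are one or two degrees of freedom, the missing-data rule, and little return if r is 0.2 or less. The change should be made before outcome data are seen, because covariates chosen afterwards would weaken the result's credibility.

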#### 4. After Discharge:

- Patients will record the following information after discharge up until 96 hours from their surgery:
  - VAS scores every 6 hours
  - Pain medication consumption (dosages, times)
  - Opioid-related side effects
  - Level of satisfaction with pain management
- Study staff may conduct reminder phone calls to ensure patients complete outpatient data collection. The outcome assessor will be blinded to the treatment group.
- Patients will record their VAS pain scores again at their 1st postop appointment, which typically occurs 10-18 days after surgery.

Sample Size: There will be 60 patients in each group, for a total study population of n = 120.

Study Locations: This will be a multi-center study. The sample size will enroll 120 (to account for 15% drop out rate) patients total, with approximately 30 patients enrolled at each site. The other participating sites are as follows:

[name]  
Sports Medicine and Shoulder Service  
University of Texas, Southwestern Medical Center  
[name]  
[name]

[name]  
MedStar St. Mary's Hospital  
[name]  
[name]

[name]  
William Beaumont Army Medical Center  
[name]  
[name]

**Aim #2:** Determine the length of stay of liposomal bupivacaine compared to interscalene nerve block in patients undergoing total shoulder arthroplasty and calculate costs associated with any differentials.

- b. Study duration and number of study visits required of research participants.

Patients will be enrolled in this study for 2 weeks after their surgical date. This time frame will include their hospital stay and include their time at home after discharge up until 96 hours after their surgery, and their 2-week postop appointment data. If patients are not scheduled for their postop appointment within 10-18 days after surgery (which is standard clinical practice), the study team will call the patient to obtain their pain score and medication data. Patient names will be stored in a password-protected database for 30 days after discharge to calculate 30-day readmission rates.

Routine patient follow up is typically at 3, 6, and 12 months for the first year. Pain data and patient reported outcomes are collected at these visits as routine clinical care. Patients routinely complete the ASES and EQ-5D questionnaires at their 12 month follow up appointment.

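### The longitudinal VAS model names only a patient random effect and no residual covariance; with 16 six-hourly scores and decaying correlation, its omnibus test would reject about 7-15% of the time at nominal 5%

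*Combined protocol and SAP*

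**What the plan says.** Section 7c (Study Statistics) describes the longitudinal model. Its fixed part reads: "Treatment group, time period as a categorical variable, and the interaction between treatment and time period will be included as fixed effects". For the dependence between scores of one patient, the plan offers only this: "and patient ID will be included as the random effect". It gives no random slope, residual correlation, period-specific variance, robust standard error or degrees-of-freedom method.

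Testing is in two steps. The first is a gate: "An initial omnibus test will be performed for all treatment and treatment by time interaction effects". The second step depends on its result: "If significant, the treatment by time interaction will be tested subsequently for each of the measurement periods". No other multiplicity rule is given for these follow-up tests, and no reference period is named.

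The scores come from section 4a. Inpatient: "Patient VAS scores every 6 hours after surgery". At home, six-hourly recording continues: "Patients will record the following information after discharge up until 96 hours from their surgery". A further score is taken at the first "postop appointment, which typically occurs 10-18 days after surgery".

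Section 7a makes VAS at 24 h the primary outcome. Section 7c also compares the groups at every time point by rank sum tests. These do not use the mixed model, and the plan does not make them conditional on the omnibus test.

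**The concern.** A model whose only dependence is a patient intercept, with independent residuals of equal variance, implies for patient i at periods j and k:

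- Var(Y_ij) = σ_b² + σ_e² at every period;
- Corr(Y_ij, Y_ik) = σ_b² / (σ_b² + σ_e²) for every pair of periods.

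Scores 6 h apart are thus taken to be no more alike than scores 90 h apart. That is a doubtful assumption while a single-shot block or a depot injection wears off and pain resolves. If correlation decays, the model treats slow within-patient drift as independent noise. It then understates the uncertainty of comparisons between distant periods and overstates it for neighbouring ones.

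At stake is the omnibus test, which is the only stated control on the period-by-period model tests. If its true size is well above 5%, it opens too often when the treatments do not differ. The group's retrospective study (section 3) used a repeated-measures analysis to decide which time points counted as significant, so this analysis may well shape the trial's conclusions.

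**Working it through.** **Inputs from the documents.** Six-hourly scores to 96 h give 96/6 = 16 periods. Section 7c needs 42 per arm, section 4a enrols 60 per arm, and 15% dropout leaves 60 × 0.85 = 51.

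**The plan's own figure.** The plan gives no figure for this test. The 42 per arm cannot be reproduced without assumptions: with the 1.4 cm difference as margin, one-sided 0.025 and 80% power, it needs an SD of 2.29 cm. It is used here only to set n, and the results hardly change with n.

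**Assumed, because the documents give none.** Two-sided 5%; normal scores; complete data; equal variance unless stated; correlation r per 6 h step as listed.

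**Step 1: one contrast by hand.** For a treatment-by-time contrast between periods `lag` steps apart, the true variance is proportional to 1 − r^lag. The fitted model uses 1 − r̄, where r̄ is the mean correlation over all 16 × 15 / 2 = 120 pairs. With k = (1 − r^lag)/(1 − r̄), the true size is approximately 2Φ(−1.96/√k).

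| r per 6 h | r̄ | 12 h v 6 h: k, size | 96 h v 6 h: k, size |
|---|---|---|---|
| 0.6 | 0.169 | 0.481, 0.5% | 1.202, 7.4% |
| 0.8 | 0.371 | 0.318, 0.05% | 1.535, 11.4% |
| 0.9 | 0.589 | 0.243, 0.01% | 1.932, 15.9% |

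For r = 0.8 at 96 h: r^15 = 0.035, k = 0.965/0.629 = 1.535, and 1.96/√1.535 = 1.58. Simulation agrees: 0-0.6% for the adjacent score, and 7-8%, 11-12% and 16% at 96 h.

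**Step 2: the omnibus test.** With balanced data the random-intercept fit has a closed form. Let d_t be the arm difference at period t, d̄ its mean over the 16 periods, and MS_b and MS_w the between- and within-patient mean squares. Then

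F = (n/2)[16 d̄²/MS_b + Σ(d_t − d̄)²/MS_w] / 16.

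Rejection over 20,000 null trials per row, at 42 / 60 per arm:

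| Assumed correlation | Random intercept | Unstructured (Hotelling) |
|---|---|---|
| Equal, 0.5 | 5.2% / 4.9% | 4.8% / 4.8% |
| AR(1) 0.6 | 9.3% / 9.5% | 5.0% / 4.8% |
| AR(1) 0.8 | 12.7% / 12.7% | 5.1% / 5.1% |
| AR(1) 0.9 | 14.4% / 14.9% | 4.9% / 5.4% |
| 30% intercept + AR(1) 0.6 | 9.8% / 9.7% | 5.2% / 4.9% |
| 30% intercept + AR(1) 0.8 | 12.9% / 13.1% | 5.1% / 5.4% |

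Milder decay plus noise, at 51 per arm, gives 7.2-7.4%. Clipping scores to 0-10 cm and rounding to 0.1 cm leaves the picture unchanged: 10.9-13.1% under intercept plus serial decay, 7.4% under mild decay plus noise, and 5.1% under equal correlation.

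**Step 3: what stays valid.** The treatment main effect rejects 4.9-5.2% in the constant-variance patterns. The group difference at a single period rejects 4.7-5.6% when variance is constant, because the model then has the right total variance for one score.

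**Step 4: variance changing over time.** At one period, k = SD_t² / mean(SD²).

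- Relative SD falling linearly from 1.25 to 0.75: mean square 1.024 and SD at 24 h 1.15, so k = 1.3225/1.024 = 1.29 and size 8.5% (simulated 8.6-8.8%).
- SD 1.8 cm to 24 h and 2.5 cm afterwards: mean square (4 × 3.24 + 12 × 6.25)/16 = 5.50, so k = 3.24/5.50 = 0.59 and size 1.1% (simulated 1.2-1.3%).

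The model's 24 h test can therefore be too liberal or too conservative.

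**Step 5: fewer periods.** If only four widely spaced periods enter (for example 24, 48, 72 and 96 h), the omnibus test rejects 5.1-5.7% under AR(1) 0.6, AR(1) 0.8 and 0.3 + 0.7 × 0.7^lag.

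**The case against.** The strongest reply is that the plan does not say residuals are independent; it is silent, and the sponsor might fit something better. That is fair as to the text. But a model described only by a patient random effect is ordinarily fitted as a random intercept with independent residuals, and otherwise the covariance would be chosen after the data are seen. Both cases call for the same change.

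The second reply is that the inflation depends on correlations nobody has documented and on how many periods enter. This stands. Section 7c speaks of time points for the rank sum tests but of periods for the model, and the retrospective study used four intervals. Sixteen levels is a fair reading of a six-hourly schedule, but not the only one.

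Third, the per-period follow-up may mean the group difference within each period, not a contrast against an early reference score. On that reading the follow-up tests stay near 5% if variance is constant. This also stands, and it limits the two-way errors to the contrast reading.

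A reader might infer that the primary 24 h result is compromised, or that the model's 24 h interval is necessarily too narrow. The documents do not support either. The 24 h rank sum test does not depend on this model, and the model's own 24 h test can err either way, depending on an SD pattern that is not given.

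**Conclusion.** The point holds in conditional form. On its ordinary reading, the model assumes a dependence pattern that suits 16 six-hourly pain scores poorly. If correlation decays, the omnibus test has a true size of about 7-15% instead of 5%, and contrasts against an early score range from almost never rejecting to about 16%. If correlation is equal for all pairs, or only four widely spaced periods are modelled, the test is close to nominal.

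It would go too far to say that the model's error rates are wrong without qualification. The treatment main effect is sound, and so are single-period differences under constant variance. What is affected is the gate to the model's period-by-period tests, which bear mainly on secondary outcomes.

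The figures rest on assumed correlations and SDs and on complete data; missing scores were not simulated. The change is worth making because it is cheap and protects a test the plan relies on.

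**What to change.** In section 7c, replace the patient random effect for the 6-96 h scores with an unstructured within-patient covariance and a small-sample degrees-of-freedom method (for example Kenward-Roger). Name the fallback in advance if this does not converge: either a patient random intercept plus AR(1) or exponential-in-hours residual correlation with period-specific variances, or patient-clustered robust standard errors. State which periods enter the model, and whether the per-period test is a group difference within the period or a contrast against a named reference. The 10-18 day score can stay outside this model, since the planned rank sum test already covers it.

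Support for the options differs. The unstructured test held 4.8-5.4% in every pattern, with complete data. A random intercept with AR(1) and noise held 4.0-6.0%, in three patterns of 600 trials each. The fallback with period-specific variances and the robust option were not simulated.

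The cost is a few sentences and a few lines of code. An unstructured covariance for 16 periods has 16 × 17 / 2 = 136 parameters, so it may fail to converge, especially with missing scores. The omnibus p-value will tend to be slightly less favourable. Patients, visits and sample size do not change.

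### The mixed-model follow-up, as worded, tests whether the arm difference has changed from an unnamed reference, not whether the arms differ at each period

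*Combined protocol and SAP*

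**What the plan says.** Section 7a names the primary outcome: "VAS pain score at 24 hours postop". Section 7c plans two analyses of the VAS scores over time.

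- Rank sum tests: "at each time point the difference between groups will be tested using non-parametric rank sum tests". These are not conditional on any other test.
- A linear mixed model with a random intercept for each patient. Its fixed part is given as: "Treatment group, time period as a categorical variable, and the interaction between treatment and time period will be included as fixed effects". Testing has two steps. The first is this: "An initial omnibus test will be performed for all treatment and treatment by time interaction effects". The second step, which is the one at issue here, reads: "If significant, the treatment by time interaction will be tested subsequently for each of the measurement periods".

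Scores are collected six-hourly (Section 4: "Patient VAS scores every 6 hours after surgery") until 96 hours. A preoperative VAS is also in the list that begins "The following baseline data will be collection prior to surgery". Section 7c does not name a reference period or a coding, does not say whether the preoperative score is one of the model's periods, and defines no contrast for the arm difference at a single period.

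**The concern.** In a model with treatment, categorical time and their interaction, the arm difference at a period is the treatment main effect plus that period's interaction term. The interaction term alone is a difference of differences. A test of it asks whether the gap between arms has moved since the reference, and the answer depends on which reference the analyst or the software picks.

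Two misreadings can follow if the periods are the postoperative scores. An early advantage for the block that has gone by 24 h would appear as a 24 h effect favouring liposomal bupivacaine. A benefit of the same size throughout would pass the omnibus test and then show nothing at any period. This is the plan's only model-based statement about pain at each period, including the primary one. The plan also has no rule for the case where the mixed model and the rank sum test disagree.

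**Working it through.** **Inputs from the plan.** 1.4 cm as the clinically important difference; 42 per group from the power analysis; 60 per group enrolled; 15% dropout; six-hourly scores to 96 h, which gives 96/6 = 16 postoperative periods.

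**Inputs assumed.** Section 7c gives no SD, alpha, power or within-patient correlation. I take two-sided 0.05 (one-sided 0.025 for noninferiority), 80% power, and correlation ρ of 0.3, 0.5 and 0.7.

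**The plan's own figure.** With n = 2·SD²·(1.96 + 0.84)²/1.4², an SD of 2.29 cm gives 42 per arm. Other choices also give 42: SD 1.98 (one-sided 0.025, 90% power), 2.58 (0.05, 80%) or 2.19 (0.05, 90%). The figure can be neither confirmed nor refuted; 2.29 cm is used below.

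**Algebra.** Let D(t) be the arm difference at time t. In the random-intercept model:

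- Direct contrast at 24 h: D(24), with SE = SD·√(2/n) = 2.29·√(2/42) = 0.50.
- Interaction at 24 h against reference r: D(24) − D(r), with SE = SD·√(2(1−ρ))·√(2/n) = 0.59, 0.50, 0.39 for ρ = 0.3, 0.5, 0.7.
- Interaction at 24 h under deviation coding: D(24) minus the mean of D over periods.

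**Full two-step procedure** (omnibus test, then follow-up), simulated with 42 per arm, 16 periods and 4,000 trials per setting. Entries are the percentage of trials with the result at 24 h, for ρ = 0.3/0.5/0.7.

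| Truth | Interaction, 6 h reference | Interaction, deviation coding | Direct contrast after the omnibus test | Rank sum test |
|---|---|---|---|---|
| 1.4 cm at 6 and 12 h, then 0 | 58/77/95 | 6/7/11 | about 5 | about 4.5 |
| Constant 1.4 cm | 5/4/3 | about 4 | 74/59/45 | about 77 |

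In the first row the interaction against 6 h estimates 0 − 1.4 = −1.4 cm although the arms do not differ at 24 h. Under deviation coding it estimates 0 − (2 × 1.4)/16 = −0.175 cm, so the false flag is much rarer. In the second row it estimates 1.4 − 1.4 = 0 under either coding. The omnibus test is passed there in 89/67/49% of trials, yet the follow-up finds nothing beyond chance.

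**A second setting**: 60 × 0.85 = 51 per arm, SD 2.3 cm, 6 h reference and four correlation patterns (compound symmetry 0.5, AR(1) 0.8, and two mixed patterns).

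- Early difference of 1.4 cm at 6 h and 0.7 cm at 12 h, then none: 24 h flagged in 55-76%, against 4-5% for the direct contrast after the same omnibus test.
- Same profile with 96 h as reference: 4-10%. The choice of first or last period as reference decides the answer.
- Constant 1.4 cm: interaction significant in 2-4%, direct contrast in 67-75%.

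**Preoperative score as reference.** Randomisation makes the expected arm difference at the reference zero, so the interaction has the same expectation as D(24). Ignoring the omnibus test, with 42 per arm, it rejects in 5% when D(24) = 0 and in 66/80/95% when D(24) = 1.4, against 80% for the direct contrast. The SE ratio to the direct contrast is √(2(1−ρ)) = 1.18, 1.00, 0.77: less precise below ρ = 0.5, more precise above it.

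**The case against.** The strongest reply is that the 24 h difference is already tested directly. The rank sum tests cover every time point, need no omnibus result and depend on no coding. This stands. A reader might infer that the trial would miss a constant effect at 24 h, or would have only a misleading test there. The documents do not support that: in the same simulations the rank sum test flags 24 h in about 4.5% of trials with no difference and about 77% with a constant 1.4 cm.

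Second, per-period treatment contrasts may have been meant. Under reference coding one period gets no test, which sits badly with a promise to test every period. The omnibus test over all treatment and interaction terms steps down naturally to arm differences. Section 3 also reports the earlier cohort's repeated-measures results as arm differences at single intervals (18-24 h and 27-36 h). This is plausible, but the sentence still names a different quantity. Section 3 also shows a risk: there the repeated-measures result qualified the 27-36 h comparison, and a repeat of that practice would let a misdirected follow-up qualify a sound rank sum result.

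Third, the large percentages need a 6 h reference and an early difference, and the plan states neither. The retrospective data show no significant early difference (P = .99 at 0-1 h, P = .208 at 8-14 h). If the early difference is near zero, the interaction against an early reference is close to the 24 h difference and neither error is large. This limits the size of the problem but not its direction.

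A reader might also infer that a preoperative reference always costs precision. That holds only when the correlation is below 0.5, and the documents give no correlation.

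**Conclusion.** The concern holds for the mixed-model follow-up as worded, and should be fixed; it is not a must-fix. The step tests a difference of differences against an unnamed reference. With postoperative periods only, it can flag 24 h when the arms differ only early: roughly 55-95% of trials with a 6 h reference, depending on correlation and profile, and about 6-11% with deviation coding. It detects a constant 1.4 cm difference at 24 h in about 2-5%.

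These sizes rest on an SD of about 2.3 cm, two-sided 0.05, complete normal data, and the stated correlations and effect profiles, none of which the plan gives. The algebra, and the missed constant effect under reference or deviation coding among postoperative periods, do not depend on them. With the preoperative score as reference both errors largely disappear. The direct rank sum comparison at 24 h is unaffected, so the damage is limited to what the longitudinal model reports and how it is read.

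**What to change.** Replace the follow-up sentence in Section 7c with: *If the omnibus test is significant, the treatment difference (main effect plus interaction) will be estimated and tested from the mixed model at each measurement period as a contrast of model means, with 95% confidence interval.* Add one overall test of the interaction to describe whether the difference changes over time. State whether the preoperative score is a period in the model.

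This keeps the existing omnibus condition, which should not be dropped unnoticed: it is the mixed model's only stated guard over about 16 periods. It has a price. For a constant 1.4 cm difference with 42 per arm, the direct 24 h contrast is significant in 74/59/45% of trials after the omnibus test, against 80% without it.

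The cost is a line or two of text and a contrast statement in the code, with no new data. It should be settled before the data are analysed, because a reference chosen afterwards could depend on the results.
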